6.0 STUDY PROCEDURES AND SCHEDULE

6.1 Screening Phase

Each potential patient will be examined before the start of the study to determine their eligibility for participation. The following investigation will be performed:

- (1) **iSTAT creatinine to determine GFR** per standard of care.
- (2) **Pregnancy Test** (if indicated) – within 1 day of mammography per routine protocol.

7.0 EFFICACY AND SAFETY [

7.1 Efficacy Measurements

FFDM and DE CE digital mammography efficacies will be assessed by pathologic diagnosis when appropriate or by one-year follow-up mammography.

7.2 Safety Monitoring

Safety will be monitored throughout the study by physical examinations, review of AEs.

7.2.1 Adverse Events

7.2.1.1 Definitions

7.2.1.1.1 Adverse Event Definition

An **adverse event** is any untoward medical occurrence in a patient administered a pharmaceutical product, which does not necessarily have a causal relationship

with the treatment. An AE can be any unfavorable and unintended sign (eg, including an abnormal laboratory finding), symptom, or disease temporally associated with the use of the study drug, whether or not it is considered to be study drug related. This includes any newly occurring event or previous condition that has increased in severity or frequency since the administration of study drug.

7.2.1.1.2

Serious Adverse Event Definition

A **serious adverse event** is any adverse event, occurring at any dose and regardless of causality that:

- Results in **death**.
- Is **life-threatening**. Life-threatening means that the patient was at immediate risk of death from the reaction as it occurred, ie, it does not include a reaction which hypothetically might have caused death had it occurred, ie, it does not include a reaction which hypothetically might have caused death had it occurred in a more severe form.
- Requires inpatient **hospitalization or prolongation of existing hospitalization**. Hospitalization admissions and/or surgical operations scheduled to occur during the study period, but planned prior to study entry are not considered AEs if the illness or disease existed before the patient was enrolled in the trial, provided that it did not deteriorate in an unexpected manner during the trial (eg, surgery performed earlier than planned).
- Results in **persistent or significant disability/incapacity**. Disability is defined as a substantial disruption of a person's ability to conduct normal life functions.
- Is a **congenital anomaly/birth defect**.
- Is an **important medical event**. An important medical event is an event that may not result in death, be life-threatening, or require hospitalization but may be considered an SAE when, based upon appropriate medical judgment, it may jeopardize the patient or subject and may require medical or surgical intervention to prevent 1 of the outcomes listed in the definitions for SAEs. Examples of such medical events include allergic bronchospasm requiring intensive treatment in an emergency room or at home, blood dyscrasias or convulsions that do not result in inpatient hospitalization, or the development of drug dependency or drug abuse.

Clarification should be made between the terms “serious” and “severe” since they are not synonymous. The term “severe” is often used to describe the intensity (severity) of a specific event (as in mild, moderate, or severe myocardial infarction); the event itself, however, may be of relatively minor medical significance (such as a severe headache). This is NOT the same as “serious”, which is based on patient/event outcome or action criteria described above and are usually associated with events that pose a threat to a patient’s life or functioning. A severe AE does not necessarily need to be considered serious. For example, persistent nausea of several hours duration may be considered severe nausea but not an SAE. On the other hand, a stroke resulting in only a minor degree of disability may be considered mild, but would be defined as an SAE based on the above noted criteria. Seriousness (not severity) serves as a guide for defining regulatory reporting obligations.

7.2.1.2 Procedures for Recording and Reporting AEs and SAEs

All AEs spontaneously reported by the patient and/or in response to an open question form study personnel or revealed by observation, physical examination or other diagnostic procedures will be recorded on the appropriate page of the CRF. Any clinically relevant deterioration in laboratory assessments or other clinical findings is considered an AE and must be recorded on the appropriate pages of the CRF. When possible, signs and symptoms indicating a common underlying pathology should be noted as 1 comprehensive event.

All SAEs that occur during the course of the study, as defined by the protocol, must be reported by the investigator to the Principal Investigator or Designee at the UAB Clinical Study Unit by faxing ([contact]) the SAE Form **within 1 working day** from the point in time when the investigator become aware of the SAE. In addition, all SAEs including all deaths, which occur up to and including 30 days after administration of the last dose of treatment must be reported to the Principal Investigator or Designee at the UAB clinical Study Unit within 1 working day. All SAEs and deaths must be reported whether or not considered causally related to the study treatment.

The SAE form, which is a component of the CRF, will be provided to each clinical trial site. The information collected includes a minimum of the following: patient identification number, a narrative description of the event and an assessment by the investigator as to the intensity of the

event and relatedness to the study treatment. Follow-up information on the SAE may be regulated by the Principal Investigator or Designee.

If there are serious, unexpected adverse drug reactions associated with the study treatment the Principal Investigator or Designee will notify the appropriate regulatory agency(ies) and all participating investigators on an expedited basis. It is the responsibility of the investigators to promptly notify the IRB of all unexpected serious adverse drug reactions involving risk to human patients.

Planned hospital admissions or surgical procedures for an illness or disease that existed before the patient was enrolled in the trial or before study drug was given, are not to be considered AEs unless they occur at a time other than the planned date.

For both serious and non-serious AEs, the investigator must determine both the intensity of the event and the relationship of the event to study drug administration.

Intensity for each AE will be determined by using the NCI CTC, Version 3.0 as a guideline, wherever possible. The criteria are provided in Appendix B. In those cases where the NCI CTC criteria do not apply, intensity should be defined according to the following criteria:

Mild	Awareness of sign or symptom, but easily tolerated
Moderate	Discomfort enough to cause interference with normal daily activities.
Severe	Inability to perform normal daily activities.
Life Threatening	Immediate risk of death from the reaction as it occurred.

For grading of abnormal laboratory AEs (grades 1-4), please see the NCICTC in Appendix B.

Relationship to the study treatment will be determined as follows:

None	No relationship between the experience and the administration of study treatment; related to other etiologies such as concomitant medications or patient's clinical state.
Unlikely	The current state of knowledge indicates that a relationship is unlikely.

Possible	A reaction that follows a plausible temporal sequence from administration of the study treatment and follows a known response pattern to the suspected study treatment. The reaction might have been produced by the patient's clinical state or other modes of therapy administered to the patient.
Probable	A reaction that follows a plausible temporal sequence from administration of the study treatment and follows a known response pattern to the suspected study treatment. The reaction cannot be reasonably explained by the known characteristics of the patient's clinical state or other modes of therapy at follows a plausible temporal sequence from administration of the study treatment and follows a known response pattern to the suspected study treatment and can be confirmed with a positive re-challenge test or support laboratory data.
Definite	A reaction that follows a plausible temporal sequence from administration of the study treatment and follows a known response pattern to the suspected study treatment and can be confirmed with a positive re-challenge test or supporting laboratory data.

Monitoring of Adverse Events and Period of Observation

Adverse events, both serious and non-serious, and deaths will be recorded on the CRFs up to 30 days after administration of the last dose of study treatment. All SAEs should be monitored until they are resolved or are clearly determined to be due to a patient's stable or chronic condition or intercurrent illness(es).

Any SAE that occurs at any time after completion of study and the designated Follow-up Period, which the investigator considers to be related to study medication, must be reported to the Principal Investigator or Designee at the UAB Clinical Study Unit.

Procedures for Reporting Pregnancy Exposure and Birth Events

If a woman becomes pregnant or suspects she is pregnant while participating in this study, she must inform her treating physician immediately and discontinue treatment. The Principal Investigator or Designee must also be contacted immediately. The pregnancy must be followed through delivery or final outcome for SAEs.

8.0 STATISTICAL METHODS

- The primary endpoint of this study is to determine the accuracy of DE CE mammography when compared to full field digital mammography (FFDM) in patients with increased breast density (BI-RADS category c or d breast density).
- The statistical analysis will focus on calculations will be performed for sensitivity, specificity, negative predictive value, positive predictive value 1 for call back (PPV1), positive predictive value 3 for biopsy performed (PPV3), cancer detection rate, false negative rate, and call back rate.

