3.0 STUDY DESIGN OVERVIEW

3.1 Study Design

The proposed prospective pilot study will invite women meeting eligibility criteria to undergo screening digital mammography and DE CE digital mammography. This trial is unique because to our knowledge this technology has not been assessed in women with BI-RADS category c and d dense breasts as an adjunct to routine screening. We will determine the potential of this imaging technique as an alternative or adjunct to screening mammography in this patient population. Patients will undergo bilateral digital mammography with 4 views and DE CE digital mammography.

[figure not shown]
We hypothesize that DE CE digital mammography will have improved diagnostic accuracy when compared to FFDM in patients with increased breast density. Sensitivity, specificity, positive predictive values (PPV1 and 3), negative predictive value (NPV), call back rate, false negative rate, and accuracy will be assessed.

This imaging technique is hypothesized to improve detection of masses (particularly those that enhance post contrast administration) in patients with dense breasts; thereby decreasing the false negative rate. Additionally, the ability of this technique to demonstrate contrast enhancement of masses may decrease call back rate as compared with FFDM. This trial is unique because to our knowledge this technology has not been assessed in this group of patients and this study will provide data to prepare for a larger clinical trial to determine the accuracy of this novel imaging technique as an alternative or adjunct to screening mammography in this patient population.

Figure 1 – Study Design

SCHEMA

Patient with heterogeneously or extremely dense breasts meeting eligibility criteria consented for study.

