3.2 Endpoints

Primary:

- Sensitivity, specificity, positive predictive values (PPV1 and 3), negative predictive value (NPV), call back rate, false negative rate, and accuracy will be assessed.

Secondary:

- Each study will be interpreted by 4 radiologists with varying levels of experience blinded to results with separation of time. Interobserver variability will be assessed utilizing raw data agreement and Kappa coefficient.

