5.0 STUDY TREATMENTS

5.1 Overall Plan

The proposed prospective pilot study will invite women meeting eligibility criteria to undergo screening digital mammography and DE CE digital mammography. This trial is unique because to our knowledge this technology has not been assessed in women with BI-RADS category c and d dense breasts as an adjunct to routine screening, and to determine potential of this imaging technique as an alternative to screening mammography in this patient population. Patients will undergo either bilateral digital mammography with 4 views or bilateral digital mammography with 4 views plus DE CE digital mammography. Dual-energy CE digital mammography will be performed with bilateral craniocaudal and mediolateral oblique views at high and low energy levels. These images will be obtained after iodinated contrast administration. Intravenous injection of iodinated contrast agent (Omnipaque 350 (iohexal, GE, Shanghai, China) at a dose of 1.5 mL per kilogram of body weight will be injected at a rate of 3mL/sec (similar dose used for computed tomography studies). Standard departmental protocols for contrast administration will be followed. Imaging will begin 2.5- 5.0 min after contrast administration. Case report forms (CRFs) will be completed for each imaging study to record technique, views, dose, breast compression force, compressed breast thickness and image time. Screening digital mammogram images will be initially read by a radiologist specialized in breast imaging with 5 to 25 years of breast imaging

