experience. A different breast radiologist will read the DE CE digital mammogram with a routine screening interpretation of only the low energy views initially. Subsequently, the entire DE CE digital mammography exam will be interpreted with all images by the same reader. Readers will interpret their designated study independently blinded to the additional study and results will be documented on the CRFs. Additional clinical work up will be performed based on both studies after the initial independent reads. All lesions will be further evaluated by standard of care. Both digital mammograms and DE CE mammograms will be assessed for quality. Truth will be determined using pathologic diagnoses when available or one year negative follow-up imaging. Calculations will be performed for sensitivity, specificity, negative predictive value, positive predictive value 1 for call back (PPV1), positive predictive value 3 for biopsy performed (PPV3), cancer detection rate, false negative rate, and call back rate.

To evaluate for interobserver and intraobserver variability, all studies will be read by 2 additional radiologists blinded to truth and randomized over time to minimize memory recall. Interobserver and intraobserver variability will be assessed utilizing raw data agreement and Kappa coefficient.

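### Section 8.0 states a comparative primary endpoint but plans only the calculation of each measure, with no contrast, no interval and no use of the within-woman pairing

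*Combined protocol and SAP*

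**What the plan says.** The question is comparative wherever it is stated. The primary objective in section 2.0 sets DE CE mammography against FFDM. Section 3.1 says: "We hypothesize that DE CE digital mammography will have improved diagnostic accuracy when compared to FFDM in patients with increased breast density". Section 8.0 opens with "The primary endpoint of this study is to determine the accuracy of DE CE mammography when compared to full field digital mammography (FFDM").

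The analysis is a list. Section 8.0 continues: "The statistical analysis will focus on calculations will be performed for sensitivity, specificity, negative predictive value", then PPV1, PPV3, cancer detection rate, false negative rate and call-back rate. Section 5.1 gives the same list, and section 3.2 ends a similar one with "call back rate, false negative rate, and accuracy will be assessed". The only agreement statistics named, raw agreement and kappa in sections 3.2 and 5.1, serve the reader-variability objective.

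On design, section 3.1 says "Patients will undergo bilateral digital mammography with 4 views and DE CE digital mammography". Section 5.1 bases the clinical work-up on both studies, which fits that reading, but it also says: "Patients will undergo either bilateral digital mammography with 4 views or bilateral digital mammography with 4 views plus DE CE digital mammography". Section 5.1 assigns the initial FFDM read to one radiologist. A different radiologist reads the low-energy DE CE views and then the full DE CE examination. Two additional radiologists later read all studies.

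**The concern.** A comparison needs a stated contrast and a measure of its uncertainty, and section 8.0 supplies neither. An analyst who does exactly what it says produces one set of point estimates for FFDM and another for DE CE. Two consequences follow.

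First, separate estimates do not determine the paired result. The same two call-back rates can come from very different amounts of disagreement between the examinations, and the uncertainty of the difference depends on that disagreement.

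Second, section 3.1 says the study is to provide data for a larger trial. If that trial is also paired, its size depends on the discordance rate, which section 8.0 does not ask for. With very few cancers, a bare result such as 1 of 1 against 0 of 1 could also be read as decisive when it carries almost no information.

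**Working it through.** **The plan's own figure.** The only design number is approximately 200 women (section 4.1). No alpha, power, effect size or precision target accompanies it, so it cannot be reproduced. It is used below as n.

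**Assumptions, not in the documents.** Call-back 12% on FFDM and 8% on DE CE (the direction section 3.1 anticipates); within-woman correlation φ of 0, 0.3 or 0.5; cancer prevalence 0.3% to 1%.

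**1. Half-width of the call-back difference.**
- Variance terms: 0.12 × 0.88 = 0.1056 and 0.08 × 0.92 = 0.0736; sum 0.1792.
- Unpaired, or paired with φ = 0: 1.96 × √(0.1792/200) = 0.0587, or 5.9 points.
- Paired: subtract 2φ√(0.1056 × 0.0736) = 2φ × 0.0882 inside the root.
- φ = 0.3: 1.96 × √((0.1792 − 0.0529)/200) = 0.0493, or 4.9 points (16% narrower).
- φ = 0.5: 1.96 × √((0.1792 − 0.0882)/200) = 0.0418, or 4.2 points (29% narrower).

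For specificity, an assumed 198 women without cancer and 10% false-positive call-back on both modalities give 5.9, 4.9 and 4.2 points at the same correlations.

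**2. Equal margins, different answers.** The rates 24/200 and 16/200 always differ by 4 points. With b and c the women called back on FFDM only and on DE CE only, the approximate 95% half-width is 1.96 × √(((b + c)/200 − 0.04²)/200).

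| Called back on both | b : c | Half-width (points) | 95% interval (points) |
|---|---|---|---|
| 0 | 24 : 16 | 6.2 | −2.2 to 10.2 |
| 7 | 17 : 9 | 5.0 | −1.0 to 9.0 |
| 11 | 13 : 5 | 4.1 | −0.1 to 8.1 |
| 16 | 8 : 0 | 2.7 | 1.3 to 6.7 |

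Two columns of rates cannot tell these rows apart; the cross-tabulation can.

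**3. Sensitivity.**
- Expected cancers: 200 × 0.003 = 0.6 to 200 × 0.01 = 2.
- Chance of none: 0.997²⁰⁰ = 55% to 0.99²⁰⁰ = 13%.
- Exact 95% lower limit when all m cancers are detected: 0.025^(1/m), so 2.5% for 1 of 1 and 15.8% for 2 of 2.
- Exact two-sided McNemar with all m discordant cancers in one direction: p = 2 × 0.5^m, which is 0.0625 at m = 5 and 0.031 at m = 6. At least six are needed for p < 0.05.

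**4. If the alternative sentence in section 5.1 meant two separate groups.** With an assumed 100 women each, the half-width is 1.96 × √(0.1792/100) = 8.3 points. The method and the precision both depend on which design applies.

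**The case against.** The strongest reply is that this is under-specification in a pilot. Section 5.1 has both examinations read independently and recorded on CRFs, so the paired table, the difference and the discordance rate could all be derived later. Nothing in section 8.0 forbids a comparison, and its first bullet calls for one. This stands. A reader might infer that the study cannot answer its comparative question; the documents do not support that, because the planned data would contain the answer. What remains is that nothing commits the analyst to extract it, and the choice of contrast is left until results are known.

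A reader might also infer that an independent-samples analysis is planned and would give intervals that are too wide. No such analysis is described; no interval of any kind is.

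The pairing is not settled either, because the alternative wording in section 5.1 conflicts with section 3.1. The work-up sentence in 5.1 favours pairing, but the two sections must be reconciled before a paired method is fixed. The study schema in 3.1 was not readable in the copy used here and may bear on this. Under either design, section 8.0 still lacks a contrast and intervals.

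The precision gain is assumed, and it is zero at correlation 0. Low correlation is plausible, since different radiologists make the initial reads. That also means a within-woman contrast on those reads mixes reader with modality. Finally, a pilot does not need a battery of significance tests. That is accepted, and the fix rests on estimation.

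**Conclusion.** The point holds as a gap in the analysis plan. The comparative primary endpoint has no stated contrast, no interval and no use of the pairing described in section 3.1 and implied by the work-up in section 5.1. For call-back, the benefit of a paired interval runs from nothing at correlation 0 to a half-width of 4.2 rather than 5.9 points at 0.5. This rests on assumed rates of 12% and 8%, 200 women with both examinations, and the paired reading of the design. Specificity behaves much the same.

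The benefit does not extend to sensitivity. A reader might infer that a paired test would rescue that comparison. With about 0.6 to 2 expected cancers against a minimum of six discordant ones, it would not. The change should be made, but it is a repair to the plan and does not show that the design or data are inadequate for a paired comparison of call-back or specificity.

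**What to change.** First reconcile section 3.1 with the alternative wording in section 5.1, so that it is clear which women have both examinations. Provided the design is paired, state in section 8.0:

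- The comparison uses the initial independent reads: FFDM against the full DE CE read, not the preliminary low-energy read.
- Call-back rate, specificity and cancer detection rate are compared within woman by a paired difference with a 95% interval for paired proportions, using a method that tolerates few discordant pairs.
- The 2×2 cross-tabulation of the two modalities is reported by truth status, with discordant counts.
- Each modality's measures carry exact 95% intervals.
- Differences in PPV1, PPV3 and NPV use a method for paired predictive values, for example GEE clustered on woman, because their denominators differ by modality and a simple paired-proportion method does not apply.
- Sensitivity, and with it the false negative rate, is reported descriptively with exact intervals and no test.
- As a limitation, different radiologists make the initial reads, so the contrast includes reader differences. The additional reads serve as a sensitivity analysis.

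The cost is SAP wording and standard code. No new data are needed.
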